Executive Function (EF) and Self-Neglect (SN): Individuals who SN often suffer from dementia, depression, and pain, all associated with ED. Additionally, SN is associated with impaired social networks and refusal of care. Prior research indicates that, when self-neglecters refuse interventions of unpaid caregivers, there is progressive decline in personal, functional and environmental domains. Secondary Aims have been added to further understand the relationship of ED with psychosocial outcomes and refusal of care. Although the APT intervention is primarily directed to the caregiver, participation of the PWD in weekly homework is critical. Better understanding the relationship of these variables will help to inform later analyses. The CLOX Drawing Test will be administered to a subset of 100 consecutively enrolled subjects at baseline. It is a two part test (CLOX 1 and CLOX 2) to measure EF and global cognition. CLOX 1 is a more direct measure of EF. CLOX 1 consists of instructing the subject to draw a clock and insert the time of 1:45 using hands and numbers in a clock. Scores range from 0 to 15. A score of 10 or below on CLOX 1 indicates executive impairment. The CLOX has high inter-rater reliability estimates (CLOX 1, Pearson, s r = 0.94, CLOX 2, Pearson, s r = 0.93; both p < 0.001). The CLOX also has a high internal consistency (Cronbach; s alpha = 0.82). After adjusting for age and education level, the Executive Interview and Mini-Mental Status Examination strongly predicted CLOX 1 scores [F (4,82) = 50.7, p < 0.001; R2 = 0.71]. Refusal of care will be measured by clinician assessment at each weekly session with the following two questions: ¿¿How many weeks did the PWD participate in weekly sessions with the therapist?¿, and ¿How many weeks did the PWD participate in assigned homework?; Responses to each question range from 0-7 and will be summed and divided by the total number of sessions the caregiver participated in to determine the PWD; s rate of engagement in the intervention.

Section D: Purpose and Objectives

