In our prior and currently funded grants, we recruit patients using methods similar to those described in this proposal to identify PWD with clinically significant pain. To determine the number of patients available for this study, we asked our clinical partners to provide the number of PWD, using dementia ICD-IX codes and restricting to patients within 40 miles not living in a long-term care facility. We identified 1273 patients. Based on our prior studies, an estimated 60% of patients will meet the criterion for clinically significant pain, resulting in 764 existing eligible patients; broadening inclusion criteria to include pain-related features will result in even more eligible patients. On the basis of our prior recruitment data, we predict excluding approximately 30% of patients due to severe dementia, history of aggression, or lack of eligible caregiver. Thus, we estimate that 535 will meet all selection criteria. In our current APT study, we have had a consent rate of 80-90%. To conservatively estimate, an 80% consent rate results in 428 patients.

One-hundred consecutively enrolled subjects will be asked to do the CLOX Drawing Test at baseline to achieve our secondary objectives. This will give adequate power to detect significant differences of small to medium magnitude in outcomes between those with and without executive function (ED). Given an N of 100 and an alpha of 0.05, there is 97% power to detect a medium effect (F2 = 0.15) and 80% power to detect an effect size for ED (over and above two covariates) as small as F2 = 0.08.

Expected Recruitment Efforts and Minimization of Attrition. In our current VA Study and prior studies, we were able to enroll 6-8 dyads per month. In the VA study and others that we completed with PWD and their caregivers, attrition is about 10%; therefore, we plan to recruit 220 dyads, 6 patients per month over 37 months. We expect we will need to contact approximately 300 dyads using our partial HIPPA Waiver in order to enroll 220 dyads in the study.

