Secondary Hypotheses 3: PWD who screen positive for ED will report significantly higher rates of pain (Philadelphia Geriatric Pain Intensity Scale), caregiver-patient related problems (Mutuality Scale), depression (30-item Geriatric Depression Scale) and behavior problems (Revised Memory and Behavior Checklist). Differences between those with and without ED in 1) pain, 2) mutuality, 3) depression, and 4) behavior problems will be evaluated with a series of multiple

linear regression models. Four models will be conducted, one for each outcome, with ED as the primary predictor and gender and caregiver relationship as covariates.

Secondary Hypotheses 4: PWD who screen positive for ED will have significantly lower engagement in intervention than PWD who do not screen positive for ED. An additional linear regression model will be conducted to test for differences between those with and without ED in engagement (Aim 2).

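### The executive dysfunction models can compare screen groups but, without age and a cognition or severity measure, cannot attribute a difference to executive dysfunction itself

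*Combined protocol and SAP*

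**What the plan says.** **Models.** In the data analysis part of Section G, Secondary Hypothesis 3 has four linear regressions (pain, mutuality, depression, behavior problems), each "with ED as the primary predictor and gender and caregiver relationship as covariates". For Secondary Hypothesis 4 the text is "An additional linear regression model will be conducted to test for differences between those with and without ED in engagement", and no covariates are listed.

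**Power.** Section G1 gives, for 100 subjects at alpha 0.05, 97% power at f² = 0.15 and "80% power to detect an effect size for ED (over and above two covariates) as small as F2 = 0.08".

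**Exposure.** Section C (Executive Function and Self-Neglect) defines ED: "A score of 10 or below on CLOX 1 indicates executive impairment". Of the CLOX as a whole it says "It is a two part test (CLOX 1 and CLOX 2) to measure EF and global cognition". It also reports that, after adjustment for age and education, "the Executive Interview and Mini-Mental Status Examination strongly predicted CLOX 1 scores", with F(4,82) = 50.7 and R² = 0.71.

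**Other relevant data.** Screening (F2) collects the FAST caregiver interview and the MIS-T, and F2 says screening answers are kept as research data. Demographic information is collected at the assessments. No planned analysis uses CLOX 2.

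**General covariate rule.** Under attrition and missing data in Section G, baseline variables that differ between APT and EU-PC at p < .25 enter all later multivariate models, as covariates or propensity scores.

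**The concern.** ED groups are not randomized. By the protocol's own account, a low CLOX 1 score goes with poorer global cognition, and the cited validation model adjusted for age and education. A PWD who screens positive is therefore likely to differ from one who screens negative in overall severity, and perhaps in age and education.

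Severity may also be related to the outcomes. For engagement the protocol says so: the description of APT in F2 makes PWD involvement in sessions optional, according to dementia severity and willingness. For pain, mutuality, depression and behavior problems the link is plausible, but the documents do not quantify it.

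What is at stake is how a significant ED coefficient is read. With only gender and caregiver relationship in the model, it could reflect executive dysfunction, more advanced dementia, older age, or a mixture. Section C describes CLOX 1 as the more direct of the two parts for executive function, so an ED-specific reading is likely to be made. The primary hypothesis is not affected.

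**Working it through.** **1. Reproduce the stated power.** Inputs from G1 and Hypothesis 3: N = 100, two-sided alpha 0.05, ED tested with 1 df, 3 predictors. Residual df = 100 − 3 − 1 = 96, noncentrality λ = N·f², critical F(1, 96) = 3.94.
- f² = 0.15: λ = 15, power 96.95% (stated 97%).
- f² = 0.08: λ = 8, power 79.96% (stated 80%).

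The figures are right for the two-covariate model at N = 100.

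**2. What R² = 0.71 can show.** F = (R²/4) / ((1 − R²)/82) = (0.71/4) / (0.29/82) = 50.2, close to the stated 50.7. So 0.71 appears to belong to the whole four-term model (apparently age, education, Executive Interview and Mini-Mental). It supports a link between CLOX 1 and global cognition but does not isolate the size of that link.

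**3. Does the p < .25 rule help?** It tests APT against EU-PC. Read literally, it could bring age or a severity measure into the ED models, but only if the randomized arms happened to differ on them. It does not look at differences between ED groups.

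**4. How confounding would act (illustration).** Suppose ED has no effect of its own. Let severity correlate r₁ with ED and r₂ with the outcome; both are assumed, as neither is in the documents. The induced correlation is r = r₁·r₂, with f² = r²/(1 − r²). Chance that the planned model is significant at N = 100:

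| r₁ | r₂ | r | f² | P(significant) |
|---|---|---|---|---|
| 0.3 | 0.2 | 0.06 | 0.0036 | 9% |
| 0.5 | 0.3 | 0.15 | 0.0230 | 32% |
| 0.7 | 0.4 | 0.28 | 0.0851 | 82% |

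The nominal rate is 5%.

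**5. Cost of adjusting.** Three added covariates (age, one cognition or severity measure, education) make 6 predictors and 93 residual df. At an unchanged partial f² of 0.08, power is 79.9%, so the lost degrees of freedom cost almost nothing. The cost comes from overlap. If the added covariates explain a share R² of ED, and the partial f² shrinks to f²·(1 − R²):

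| Assumed R² | f² from 0.08 | Power | f² from 0.15 | Power |
|---|---|---|---|---|
| 0 | 0.080 | 80% | 0.150 | 97% |
| 0.2 | 0.064 | 71% | 0.120 | 93% |
| 0.5 | 0.040 | 51% | 0.075 | 77% |

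As a detectable difference, d = √(0.08 / (q(1 − q)(1 − R²))), where q is the share screening positive (not given in the documents). At q = 0.5, d rises from 0.57 SD (R² = 0) to 0.63 (0.2) or 0.80 SD (0.5). At an 80/20 split it rises from 0.71 to 0.79 or 1.00 SD.

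**6. Hypothesis 4.** Section C measures engagement by PWD participation in therapist sessions and homework, and Section D refers to engagement in APT. Under 1:1 allocation about 50 of the 100 CLOX subjects are in APT. At N = 50, power is about 76% at f² = 0.15 and 50% at f² = 0.08 before any overlap. The 32% in step 4 becomes about 18%.

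**The case against.** **The aim is descriptive.** Section D sets out to examine relationships, and the association of ED with engagement. Hypotheses 3 and 4 compare screen-positive with screen-negative PWD. A reader might infer that the planned models cannot answer their own question. The documents do not support that: the models do answer the screen-group question, and no passage claims an effect of ED independent of severity. This objection stands, and it limits the point to interpretation.

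**Confounder or component.** Executive loss is part of dementia, functional stage may partly follow from it, and CLOX 2 is the other half of the same test. Adjustment could remove real ED association. This also stands. Which model should be primary is a matter of judgement, and it is a reason to show both.

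**Restricted severity.** Enrolment is limited to mild-to-moderate dementia, with FAST not above 6. This narrows the severity range and makes the upper end of the illustration less likely, but severity still varies.

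**Direction.** Section C says pain is under-identified in PWD. Greater severity could lower reported pain and mask an ED association, so the bias need not produce false positives.

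**Hypothesis 4.** Its covariates are unstated. It is under-specified, and cannot be said to have deliberately left severity out.

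**Conclusion.** The point holds as a limit on interpretation. The Hypothesis 3 models, and the Hypothesis 4 model as far as it is specified, can show that PWD who screen positive for ED differ from those who do not. They cannot attribute the difference to executive dysfunction rather than age or overall severity, and the p < .25 rule does not change that.

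Two stronger readings are tempting. One is that R² = 0.71 measures how far global cognition drives CLOX 1; it does not, because it fits the four-term model as a whole. The other is that the false-positive rate is 9% to 82%. That range is illustrative only: it rests on correlations absent from the documents and on N = 100, which does not appear to apply to Hypothesis 4.

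The power figures for the adjusted model (about 71% or 51% at f² = 0.08) rest on assumed overlaps of 20% or 50% and on the partial f² shrinking in proportion. These are secondary aims in a non-randomized comparison. The change is worth making but is not critical to the trial.

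**What to change.** Before analysis, pre-specify one additional model for each of the four Hypothesis 3 outcomes and for Hypothesis 4. It should contain ED, gender, caregiver relationship, age and one named, already collected measure of global cognition or severity (CLOX 2, or MIS-T or FAST from screening). Add education if the demographic form records it, since the documents never list it. State the planned covariates for Hypothesis 4, which are now blank.

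Report the two models side by side. Use the planned model for the screen-group comparison, and base any ED-specific conclusion on the adjusted one.

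In G1, say that 97% and 80% apply to the two-covariate model at N = 100. Give the adjusted-model power under stated overlap assumptions; changing only the number of covariates in the sentence would hide the loss. State separately how many subjects Hypothesis 4 is expected to have.

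The cost is SAP wording and five extra regressions, with no new data collection (education only if already recorded). The downside is wider intervals and possible over-adjustment, which is why both models are shown.

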If subjects will be paid (money, gift certificates, coupons, etc.) to participate in this research project, please note the total dollar amount (or dollar value amount) and distribution plan (one payment, pro-rated payment, paid upon completion, etc) of the payment.

Dollar Amount:

100

Distribution Plan:

Caregivers will receive \$25.00 for each of the 4 assessment interviews. These recruitment methods have been previously approved by the BCM institutional review board. Patients will not be reimbursed as their involvement with research assessments is minimal.

Section M: Genetics

How would you classify your genetic study?

Discuss the potential for psychological, social, and/or physical harm subsequent to participation in this research. Please discuss, considering the following areas: risks to privacy, confidentiality, insurability, employability, immigration status, paternity status, educational opportunities, or social stigma.

Will subjects be offered any type of genetic education or counseling, and if so, who will provide the education or counseling and under what conditions will it be provided? If there is the possibility that a family's pedigree will be presented or published, please describe how you will protect family member's confidentiality?

Section N: Sample Collection

None

Section O: Drug Studies

Does the research involve the use of ANY drug* or biologic? (*A drug is defined as any substance that is used to elicit a pharmacologic or physiologic response whether it is for treatment or diagnostic purposes)

No

Does the research involve the use of ANY gene transfer agent for human gene transfer research?

O1. Current Drugs

Is this study placebo-controlled?

Νo

Will the research involve a radioactive drug?

No

Section P: Device Studies

Does this research study involve the use of ANY device? No

Section Q. Consent Form(s)

None

Section R: Advertisements

Mode of Advertising: Other: Clinics, Day Centers, and Community Events

Exact language of Advertisement:

See Flyers and FACT Sheets attached in Section S. These will be posted at Day Centers and handed out by study-staff or BCM or Kelsey-Seybold Providers when recruiting patients out of the clinics. They will also be distributed at community events such as the BCM Update on Alzheimer's.

The following print ad will be posted in Day Center newsletters:

Baylor College of Medicine is looking for patients with dementia to participate in a clinical trial of an educational intervention designed to help their caregivers improve identification and management of their pain and distress. Investigators hope this will help prevent the onset of certain behavioral symptoms that may occur in patients with dementia. Patients may qualify if they are experiencing pain, depression, or a strained relationship with their caregivers and currently receive clinical care from Baylor Geriatrics Associates, Baylor Alzheimer¿s Disease and Memory Disorders Center, or Kelsey-Seybold Clinics. Study visits are conducted either in-home or by telephone. For more information, please contact [name], BS at [contact] or [contact].

A 4X6 inch tent card with study information will be displayed at the clinics of our clinical partners as well as at dementiaspecific day centers and community event. See proof attached in Section S.

Addendum to Section J2 Consent Procedures

A telephone script will be used to obtain verbal consent to administer the initial protocol screening, which will assess the presence of an eligible caregiver; clinically significant pain, depression or PWD/caregiver relationship difficulties; dementia of mild-moderate severity; absence of aggression; and willingness of PWD and caregiver to participate.

Participant written informed consent for eligible and willing PWD and caregivers will be obtained in person or by mail immediately after the initial telephone screening appointment. These recruitment methods have been previously approved by the BCM institutional review board. Verbal permission to use the answers to the telephone screening questions for the research will have been obtained from the PWD and caregiver prior to collection of this data. Participants will be reminded of this at the time of inperson written informed consent. No other research procedures will take place until the consent forms have been signed and subjects have received the signed copies. See Section S for "Procedures for Consent by Mail."

Particular effort will be made to recruit women and minorities via fliers (representing different genders and races) and specific recruitment through the participating clinics. We will use the expertise of other investigators and community practitioners as "cultural guides" should we identify challenges in recruitment or retention of the racial and ethnic minorities. Study administrative staff will be trained to consider and respect different attitudes, preferences, and communication styles of minorities, women, and older adults. In our prior studies, we have had 20% minority recruitment, which is similar to the prevalence of minorities in the older veteran population from which we were recruiting.
